## **VI. BIOSTATISTIC ANALYSIS**

### **Aim 1:**

We will use qualitative interviews and exit interviews to identify further understand the patient flow and clinic structure at each site, assess surgeon and staff perceptions and barriers and facilitators for study implementation and referrals, provide description of the TOR skills and perception of the utility of the TOR components (including suggestions for potential modifications), understand surgeon and medical staff beliefs and attitudes toward biopsychosocial care at each site, and learn barriers and facilitators for making patient referrals. The qualitative focus group data and individual exit interview data will be transcribed and analyzed, using NVivo 10 qualitative software, and we will conduct thematic content analysis using guidelines provided by Miles and Huberman. The 2 coders (study clinicians) will meet on an ongoing basis with [name] and [name] to discuss the structural thematic framework, categories, and coding plan, guided by the Proctor Framework, but allowing for the emergence of additional codes. To ensure coding reliability, coding discrepancies will be resolved through discussion and comparison of raw data. Coding will continue until a high reliability ( $Kappa > 0.80$ ) is established. Once these data analyses are completed, the multidisciplinary team will provide the expert review of data, to discuss the interpretation of our findings in the context of current research on chronic heterogeneous pain. We will also work on identifying whether site specific themes emerged that would require tailoring the training materials as well as staff training and methodology for aim 2 to each site.

### **Aim 2:**

The main purpose of this multi-site feasibility RCT is to assess feasibility, acceptability, appropriateness and fidelity of TOR and study procedures at each of the 4 sites, to meet benchmarks before an efficacy trial. We will calculate, for each site, number of patients identified via medical record, number referred by surgeon, number screened, number consented, number enrolled and randomized. The results will be reported using descriptive statistics (numbers, proportions, and mean scores).

Given the feasibility RCT design, the trial is not fully powered for efficacy. Consistent with the feasibility design of this trial, we will report means and SDs of all measures at all time points, including distribution of scores and internal consistency. To determine the measures' sensitivity to detect change, we will report within group change in all quantitative outcomes. We will also conduct exploratory between group analyses to inform the future fully powered RCT.

## **VII. RISKS AND DISCOMFORTS**

### **Aim 2:**

The greatest discomfort associated with participation is the time required to complete the questionnaires and grip strength and walk test measurements. Subjects might experience minimal pain when completing these tests. Study physicians will be readily available should a subject experience discomfort while completing the measurements. The grip strength and walk test are

optional and subjects can refuse participation. Questionnaires and measurements will require approximately 25 minutes at the time of enrollment and about 25 minutes at the 3-month follow-up.

Patients are not obligated to answer any question. The patient's participation will not affect their medical care. Patients can withdraw from the study at any time. Patients who are disturbed by any of the questions will be offered psychological counseling, referral to a psychiatrist, or immediate transfer to the emergency room for psychiatric evaluation, depending upon the severity of the reaction.

Study physicians will be readily accessible for consultation should a study patient experience increasing discomfort while completing the questionnaire or during the intervention time period. In the extremely unlikely event that a patient has a severe adverse emotional disturbance while completing the questionnaire, we will contact the Acute Psychiatric Service and immediately take the patient to the Emergency Department for treatment. Subjects removed to the Emergency Department for additional care will not be asked to complete the questionnaires and will be dropped from the study.

## **VIII. POTENTIAL BENEFITS**

**Aim 1:** No direct benefit is anticipated.

**Aim 2:** No direct benefit is anticipated. Participants may improve their ability to cope with pain and improve their mood, pain, and disability. Information gained through this study may lead to a better understanding the importance of delivery method of mind body interventions.

## **IX. MONITORING AND QUALITY ASSURANCE**

Electronic information will be stored in REDCap (Research Electronic Data Capture), a free, secure, and HIPAA-compliant web-based application hosted by the Partners HealthCare Research Computing Enterprise Research Infrastructure & Services (ERIS) group (based at the PHS Needham corporate datacenter). Data will be stored on password protected computers that will be stored in secure locations at all times. Paper data files (with coded subject identification) will be stored in a locked filing cabinet. Only research staff will have access to these data locations.

A unique anonymous identifier will be assigned to each subject; subsequently, all data collected will be associated exclusively with this identifier. This includes all questionnaires administered over the course of the study, as well as home practice logs.

Data from this study will be stored for three years after the publication of all study results, at which time all paper data files will be shredded, and computer files will be deleted.

The following study staff will be blinded: 1) overall PI; 2) site PIs; 3) surgeon champions; 4) study statistician; 5) RA involved with any post and follow up self-report and objective assessments; 6) statistician who is performing blinded analyses.

To achieve RA blindness, treatment assignment will be done by randomization RA, who will not be directly involved in evaluation or data collection. Survey data collection will be conducted by another RA who will be blinded to participant treatment assignment. Participant self-report surveys will be implemented using secured online survey software, which will significantly limit the potential of the RA to introduce bias. The overall PI, site PIs and surgeon champions will not be involved in the group assignment or collection of data. Also analyses will be conducted when data are unlocked. The study statistician and statistician who perform blinding analysis will not have access to randomization algorithm key.

The following study staff will not be blinded: 1) randomization RA (RA who will randomize participants after consent and baseline and give participants study materials consistent with their respective treatment arm, and problem solves in real time and potential tech issues for those in TOR); 2) study therapists/clinicians; 3) the statistician who will develop the randomization scheme. The unblinded staff will have no access to data and no involvement in data monitoring and analyses.

### **Data Management and Quality Control Procedures**

To maximize accuracy and security, all survey data will be collected and stored on REDCap. Research staff will ensure that proper consent has been obtained before sending the REDCap survey to each participant.

REDCap (Research Electronic Data Capture) is a free, secure, HIPAA compliant web-based application hosted by the Partners HealthCare Research Computing Enterprise Research Infrastructure & Services (ERIS) group. Vanderbilt University, with collaboration from a consortium of academic and non-profit institutional partners, has developed this software toolset and workflow methodology for electronic collection and management of research and clinical study data. Data collection projects rely on a study-specific data dictionary defined by members of the research team with planning assistance from Harvard Catalyst, The Harvard Clinical and Translational Science Center EDC Support Staff. This iterative development and testing process results in a well-planned data collection strategy for individual studies. Using REDCap, the research team can also design web-based surveys and engage potential respondents using a variety of notification methods. REDCap provides flexible features that can be used for a variety of research projects and provides an intuitive interface to enter data with real time validation (automated data type and range checks). The system offers easy data manipulation with audit trails, reports for monitoring and querying participant records, and an automated export mechanism to common statistical packages (SPSS, SAS, Stata, R/S-Plus).

Since consistency of application of the study protocol is critical to acquiring high quality data, all research personnel have undergone or will undergo a competency-based training program prior to enrolling subjects.

### **Data and Safety Monitoring Plan**

Study data will be maintained in a locked filing cabinet and on password protected computers. Questionnaires and self-reported responses will not become part of the patient's medical record

and will not contain medical record numbers or names. Hardcopies of study related data and forms will be stored in a lockable file cabinet. Patient information will remain confidential by keeping identifying information (name, medical record number, and subject number) in a separate locked file cabinet. Only the investigators and study staff specified on the consent form will have access to this information

Among the 4 recruitment sites (MGH, Dell, Kentucky, Vanderbilt), PHI will be shared related to enrolled study participants. MGH will send and receive PHI to/from Dell, Kentucky and Vanderbilt using encrypted email as well as shared storage in the Partners-approved platform Dropbox. PHI will not be shared with any study collaborators outside of MGH, Dell, Kentucky and Vanderbilt. Once data collection is completed, all data will be de-identified. Our collaborator at Brown University will receive only de-identified data.

The study research assistant will be trained in procedures to protect study participant confidentiality. All data will be kept confidential, stored on password protected drives accessed through encrypted devices, accessible only to trained study staff. Participants' data will be identified by ID number only, and a link between names and ID numbers will be stored separately and securely. Session recordings will be immediately downloaded from the recording device to the secure computer and subsequently deleted from the recording device. Recordings will be labeled with the patient ID and stored on a password protected computer; the recording will be subsequently and immediately deleted from the recording device. Just like a regular doctor's appointment, the live-video visit will be kept private and confidential. The research team will report to the data safety and monitoring committee with details of any participant confidentiality breach and corresponding plans for corrective action. Data for all participants will be kept strictly confidential, except as mandated by law or as necessary for monitoring by IRB, or NCCIH. In the unlikely event of serious concerns of suicidality and to ensure patient safety, we will suspend confidentiality and alert the site PIs so that appropriate clinical interventions can be assured.

All study staff have been trained in responsible research conduct through a CITI course. The RAs will be trained on the importance of maintaining confidentiality through the assignment of ID numbers. All data will be kept confidential, on password protected drives accessed through encrypted devices only, accessible only to trained study staff. Participant data will be identified by ID number only, and a link between names and ID numbers will be saved separately. Session recordings will be immediately downloaded from the recording device to the secure computer and subsequently deleted from the recording device. Recordings will be labeled with the patient ID and password protected.

**Adverse Event Monitoring:** Throughout the study subjects will be monitored for the occurrence of events defined as any undesirable experience or unanticipated risk. Lack of effect of treatment is not considered an event. All adverse events will be reported on an adverse event form. The Principle Investigator has the responsibility of reporting serious adverse events (death, life threatening illness or injury, serious injury, or permanent disability) to PHRC within 24-72 hours of notification.

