TOR directly targets catastrophic thinking about pain (i.e., misconceptions about pain and activity, hopelessness, helplessness and magnification of pain) and pain anxiety (i.e., cognitive, physiological and pain avoidance elements) through teaching relaxation response and mindfulness skills, correction of misconceptions (e.g., through education and adaptive thinking techniques), acceptance and value-based engagement in activities, and activity pacing. The goal is to “confront” rather than “avoid” the pain experienced and activities that may be associated with pain and thus prevent the transition toward chronic pain. Each TOR session is about 45 minutes, and all 4 are delivered within a period of 4-5 weeks (TOR and control arm will be yoked for the timing of interventions). Brief mind-body interventions have shown to be feasible to implement and acceptable to patients in busy orthopedic practices. The live video delivery format aims to bypass established barriers to biopsychosocial care for orthopedic patients (e.g., transportation, inflexible schedules). These format/dosage considerations are all in line with feedback we received from surgeons and patients with acute orthopedic injuries during the iterative treatment development process. It is unlikely that TOR intervention causes any risk of physical or psychological harm other than potential experience of psychological discomfort while discussing their experiences during intervention sessions. As indicated, our pilot feasibility RCT of TOR at MGH showed evidence for feasibility, acceptability, and satisfaction for TOR.

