## V. STUDY PROCEDURES

**Aim 1:** Participants will be surgeons and medical staff at the original 3 sites. Participants will provide verbal informed consent prior to participation. Participants will be informed their participation is voluntary and they are not obligated to answer any questions. Next, we will conduct separate focus groups with surgeons and with the rest of the medical staff. Trauma chiefs (Co-Is on this grant) will not be included in the focus groups to avoid bias. The site PI and surgeon champion at each site, with support from the trauma chiefs will give presentations during the staff meetings to discuss the aim of the study, present preliminary data, discuss potential benefits to patients, and encourage participation. The RA at each site will next assist with recruitment, consent, and scheduling focus groups. For MGH surgeons, ideal focus groups are at 6:30 am or 7:00 am. Each site will prioritize recruitment, and the number of focus groups will depend on ability to schedule participants at each site. Exit interviews will be administered immediately after.

**Aim 2:** We will conduct a 4-site feasibility RCT and recruit 180 participants total (60 at the parent site, 50 completers; 40 per child site, 33-34 completers).

Baseline and follow-up assessments will include measurements of grip strength (for upper extremity injuries) or a walking test (for lower extremity injuries), which measures the time required to travel 10 meters, self-report measures assessing the primary (pain intensity and disability), and secondary (depression, PTSD, pain catastrophizing and pain anxiety) variables, and demographic information. Patients will complete the following reliable and valid battery of questionnaires, which will take approximately 20 minutes to complete:

- Demographics: Age, gender, race/ethnicity, education, employment, income, marital status, current psychotropic/pain medication intake, comorbid medical conditions, history of depression or other mental health conditions.
- Clinical variables: Injury type, date, location, prior pain (all by self report).
- Pain: Numerical Rating Scale, requires the patient to rate their pain on a defined scale (11-point scale from 0 (no pain) to 10 (worst pain)).
- Pain: Use of analgesics; Concomitant treatment: Daily self-report log.

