Next, following guidelines for psychosocial clinical trials, we plan for a 1:1 RCT comparing 2 arms: 1) TOR (delivered via Zoom) + MEUC and 2) MEUC. Patients will be randomized based on scores on Pain Catastrophizing (PCS) and Pain Anxiety (PASS). PCS and PASS were chosen for the randomization based on our prior work with this population, which showed that PCS was the strongest predictor of pain intensity and PASS of long term disability. This method of randomization (median split on PASS and PCS) was successful in our previous face to face RCT. We will stratify participants by site, using the randomization module in REDCap, which will be prepared using permuted blocks by the study statistician. Out of the 180 participants enrolled, 90 will be randomized to TOR and 90 to MEUC. Within the 60 participants at the parent site, 30 will be randomized to TOR and 30 to MEUC. Within each of the 40 participants at the child sites, 20 will be randomized to TOR and 20 to MEUC. We will report on our primary and secondary outcomes specifically for each site (separate by study site strata). There will be 3 assessment points for the intervention: 1) baseline (0-3 months post trauma and before the intervention), 2) first follow-up post intervention (4 weeks post baseline), 3) second follow-up post intervention (3 months post baseline).

TOR has been developed tested and found efficacious in improving disability, pain, mood and coping in patients with orthopedic trauma, and we are ready to test it via videoconferencing to improve access to care. TOR has 4 sessions, 45 minutes each. TOR is focused on 1) discussing

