Participants randomized to TOR will undergo set-up for the live video intervention prior to leaving the clinic. This includes: 1) installing Zoom and teaching participants how to use it; 2) scheduling their 4 weekly intervention sessions with the clinician; 3) setting up EZ texting to receive reminders; and 4) installing the TOR web platform (with session content and guided exercises) as an app on their phones. Participants who do not own a smart phone will be given one, and the RA will set their phone up at the first visit. We will also provide study participants with a data plan for the duration of the study, or brainstorm ways to access free internet (e.g., library, friends' houses), if needed. Our study team has used these strategies in prior studies. The RA will also schedule the participant's first session of TOR and ensure the participant writes down the date and time of the first session.

In order to ensure that participants in the TOR program are familiar with Zoom, the psychologist will schedule a brief session to go over how the software works and prepare the participants for the intervention.

Participants randomized to TOR will also receive daily text reminders through Twilio to practice program skills as well as record their skills practice if they consent to receive text reminders.

For the provider feedback surveys, surgeons and medical staff at each of the 4 sites will be asked to participate. Up to 80 providers are expected to participate. Participants will provide implied informed consent prior to participation. After reviewing a consent fact sheet, participants will be asked to complete a brief demographic questionnaire as well as a brief survey regarding their perceptions on the implementation of the TOR study in their clinic (11 items). Site PIs and surgeon champions will distribute surveys to providers at their site. We have the full support from the orthopedic leadership at each site for these activities.

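### No common way of eliciting adverse events is defined while planned study contact differs by arm, so adverse-event counts by arm may not be comparable

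*Combined protocol and SAP*

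**What the plan says.** The adverse-event plan is one short paragraph in section IX (Data and Safety Monitoring Plan, Adverse Event Monitoring). It sets a single rule for all subjects: "Throughout the study subjects will be monitored for the occurrence of events defined as any undesirable experience or unanticipated risk". It adds that "All adverse events will be reported on an adverse event form" and makes the principal investigator responsible for reporting serious events. It gives no question, schedule, look-back period or person who asks, and does not say whether the TOR sessions are a source of reports.

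Section V introduces the follow-up battery with "Patients will complete the following reliable and valid battery of questionnaires". The list covers demographics, pain, function, mood, coping and related scales, and a satisfaction questionnaire is added at 4 weeks. None of these is an adverse-event item. The nearest is a daily log of analgesics and concomitant treatment.

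On contact in the TOR arm, section V says "TOR has 4 sessions, 45 minutes each", has the research assistant "scheduling their 4 weekly intervention sessions with the clinician", and adds that "the psychologist will schedule a brief session to go over how the software works". It also says: "Participants randomized to TOR will also receive daily text reminders through Twilio to practice program skills". The Background gives the period: "Each TOR session is about 45 minutes, and all 4 are delivered within a period of 4-5 weeks". MEUC participants receive a booklet and a website. Both arms receive usual orthopedic care and are assessed at baseline, 4 weeks and 3 months.

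Two other places bear on the point. The blinding text in section IX lists the therapists among unblinded staff, who are to have no access to data and no part in data monitoring. Section VI plans descriptive reporting, within-group change and exploratory between-group analyses, and does not mention adverse events.

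**The concern.** The definition of an event is broad enough to include almost any unpleasant experience. What is recorded therefore depends heavily on how often a patient speaks with someone from the study and whether that person asks. The patients are recently injured and selected for high pain catastrophizing or pain anxiety, so such experiences could easily come up in long conversations with a clinician. Only the TOR arm has those conversations, and the plan has no common question set to offset the difference.

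Two things are at stake. A count of events by arm, carried forward to the planned efficacy trial, could make TOR look less well tolerated than it is. Separately, and whether or not the arms are compared, events in control patients are more likely to go unrecorded. A feasibility trial is the place to settle this, since testing procedures is its stated purpose.

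**Working it through.** The documents give no adverse-event rate, detection rate or safety power, so there is no figure to reproduce. The check has three parts.

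**1. Scheduled study contacts after baseline (sections I and V)**

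| | TOR | MEUC |
|---|---|---|
| Clinician sessions | 4 | 0 |
| Assessments (4 weeks, 3 months) | 2 | 2 |
| Total | 6 (7 with the set-up session) | 2 |
| Session time | 4 x 45 = 180 min | 0 min |

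The daily texts are not counted, because they are described as practice reminders and not as asking about events. Follow-up questionnaires may be completed online from home, and the grip and walk tests are optional, so an MEUC patient could have no live study contact after baseline.

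**2. Routes to the adverse event form**

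The Adverse Event Monitoring paragraph requires every event to be recorded. The blinding text keeps therapists out of data monitoring. There are two readings. If therapists do file event forms, TOR has a route that MEUC lacks. If they do not, events disclosed in sessions have no stated route to the form, and nobody is assigned to ask in either arm. Neither reading gives a defined and equal procedure.

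**3. Illustration of size**

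From the documents: 90 patients per arm, sessions over 4-5 weeks, follow-up of 3 months (taken as 13 weeks). Assumed: equal true rates, events spread evenly over time, detection dT = 0.90 in TOR during the session period, and detection dM = 0.30 to 0.70 in MEUC throughout and in TOR once sessions end.

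With w session weeks:

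Ratio TOR:MEUC = [(w/13) x dT + ((13 - w)/13) x dM] / dM

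- w = 5, dM = 0.30: (5/13 x 0.90 + 8/13 x 0.30)/0.30 = 0.531/0.30 = 1.77
- w = 5, dM = 0.50: (5/13 x 0.90 + 8/13 x 0.50)/0.50 = 0.654/0.50 = 1.31
- w = 5, dM = 0.70: (5/13 x 0.90 + 8/13 x 0.70)/0.70 = 0.777/0.70 = 1.11
- w = 4, dM = 0.30 and 0.70: 1.62 and 1.09

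The ratio does not depend on the true rate, but the counts do. At an assumed true rate of 10%, 90 x 0.10 = 9 events occur in each arm. With w = 5, the recorded numbers are:

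- dM = 0.30: 9 x 0.531 = 4.8 in TOR against 9 x 0.30 = 2.7 in MEUC
- dM = 0.70: 9 x 0.777 = 7.0 in TOR against 9 x 0.70 = 6.3 in MEUC

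With equal detection in both arms the ratio is 1 at any true rate.

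**The case against.** The strongest reply is that no biased comparison exists, because none is planned. Section VI names no safety table or test, and the trial is not powered for efficacy. That stands. A reader might infer from the unequal contact that a planned between-arm safety comparison is biased; the documents do not support that.

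A reader might also infer that events are asked about in the TOR sessions. Nothing says so, and the blinding text points the other way. The mechanism is therefore conditional on session disclosures reaching the form.

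Nor is MEUC without contact. Usual care includes meetings with surgeons and medical staff, the daily treatment log is not restricted to one arm, section VII makes study physicians accessible to any study patient during the intervention period, and the Background says that the arms are yoked on timing (what this means for MEUC is not explained). These points soften the contrast. They do not remove it: no route from usual care to the adverse event form is described, and none of them offsets TOR's extra contact.

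Absence from the questionnaire list is not proof that nobody asks, since the content and administration of the event form are not given. This also stands, but the plan should then say what that form asks, of whom and when.

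Finally, applying session-level detection to all 3 months would give ratios of 0.90/0.30 = 3.0 to 0.90/0.70 = 1.3. That is too large, because the sessions end after 4-5 weeks and scheduled study contact is equal afterwards.

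**Conclusion.** The plan leaves adverse-event elicitation undefined while giving one arm far more scheduled contact. Any tabulation by arm is therefore at risk of showing more events in TOR when true rates are equal, and control patients are less closely monitored. On the assumptions above the apparent ratio is about 1.8 to 1.1 with five weeks of sessions. The detection shares and the even spread of events are assumptions with no source in the documents, so the range shows what is plausible and is not an estimate.

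It would go too far to say that the safety result will be wrong in direction: with equal true rates there is no direction to reverse, and the size of any distortion is unknown. This is a modest point in a feasibility trial with no powered safety objective. It is worth acting on because the remedy is cheap and changes what is collected.

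**What to change.** 1. Add one identical, self-completed adverse-event question set to the REDCap forms at 4 weeks and 3 months in both arms, with a stated look-back (since baseline, then since the 4-week form). Place it after the outcome measures.
2. Have the answers reviewed by someone other than the blinded assessor, since a reply that mentions sessions would reveal the arm. Name that person in section IX, which at present bars unblinded staff from the data.
3. Use these answers for any between-arm adverse-event table.
4. Keep recording events as they arise. Report all of them in full, including those raised in TOR sessions and all serious events, labelled by source. The label can reveal the arm, so withhold it from blinded staff until follow-up closes.
5. Reconcile the blinding text and the Adverse Event Monitoring paragraph in section IX by stating whether therapists report adverse events.

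The cost is about a minute per assessment, one extra listing and a few sentences of protocol text. The drawback is that the common table relies on recall, which is why the full listing by source must stand beside it. No sample size, visit or treatment changes.
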